7.8.2 Primary Safety Objective #2

Study related serious adverse events through 12 months

Analysis Dataset:

Safety Analysis Set per section **Error! Reference source not found..**

Analysis Method:

The study-related SAE rate will be summarized for the Safety population using a Kaplan-Meier curve through at least 12 months. Analyses will include survival probabilities and 95% confidence interval bands through the 12-month visit. Subjects not completing the study will be censored after their last available visit. A sensitivity analysis shall be performed where a cumulative incidence curve is estimated and death will be accounted for as a competing risk. The cumulative incidence curve will be descriptively compared to $1-S(t)$ where $S(t)$ is the survival function estimated by the Kaplan-Meier method.

The observed cumulative incidence estimate may be calculated using the “cmprsk” library in R, with code similar to the following:

```
cmpout1 <- cuminc(time,event)
```

The event variable is 0 if censored, 1 if an event occurs and 2 if a death occurs.

Endpoint Definition:

The rate of SAEs through 12 months related to the device, study procedure, or secondary procedure to maintain or reestablish patency. For time-to-event analysis, day 0 is day of first attempted AVF creation procedure and final date is day of event or day of last follow-up. An independent CEC will assess and adjudicate any potential relationship to the device and/or procedures per the criteria set in the CEC charter.

Additional Analysis:

Subcomponents of the SAE rate endpoint will also be provided, with subcomponents defined as related to the device, related to the study procedure, or related to the secondary procedure to maintain or reestablish patency.

7.8.3 Secondary Objective #4

Overall patient safety

Analysis Dataset:

Safety Analysis Set per section **Error! Reference source not found..**

Analysis Method:

Study-related AEs occurring during the study will be presented for the Safety population cumulatively and for each of the following study intervals:

Peri-operative: within 7 days (≤ 7 days) of the AVF creation procedure

Post-operative: 8 days to 3 months after the AVF creation procedure

Follow-up: more than 3 months after the AVF creation procedure

AEs will be summarized as the number of events as well as the number and percentage of subjects experiencing one or more of the following event types:

- Any study-related AE:
 - Cumulative
 - Peri-operative
 - Post-operative
 - Follow-up
- AE related to:
 - study device
 - study procedure
 - intra-procedure (index) or planned balloon angioplasty (PTA) maturation procedures
- Cannulation-related AE
- AE resulting from or related to a secondary procedure
- SAE
- UADE
- Stenosis

SAE incidence will be summarized by system organ class and event as the number of events as well as the number and percentage of subjects experiencing each event. The above summaries will be presented cumulatively and for each study interval. For the four different study intervals, subjects are included in the denominator of percentage calculations if their follow-up has extended at least to the beginning of that study time interval. Non-SAE will be presented in manner similar to SAE.

Endpoint Definition:

All adverse events related to the device, procedure, secondary procedures to maintain or re-establish patency, or any serious adverse event shall be reported. An independent CEC will assess and adjudicate any potential relationship to the device and/or procedures per the criteria set in the CEC charter. Stenosis events will be reported based on the MedDRA terms AVF site stenosis or AVF occlusion.

Additional Analysis:

- To assess the safety of the AVF creation procedure, rates for SAEs, UADEs, and procedure-related AEs will be descriptively compared to the pre-market study (DEN170004) results by presenting the rate and 97.5% CI for each study (CI adjusted for multiple comparisons). This comparison will be presented for the peri-operative and post-operative study intervals. If there are differing representations of baseline characteristics between the two studies, they will be adjusted for in the analysis.

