## 11.5 Reporting of Adverse Events

The investigator is required to assess and document in the medical record all SAEs, ADEs, SADEs, and DDs (per the definitions in Table 5) observed in subjects from the time of study enrollment. AEs shall be followed until the event has resolved or until study exit. In case of permanent impairment, the event shall be followed until the event stabilizes and the overall clinical outcome has been ascertained.

Reporting of AEs and DDs shall end once the subject exits the study. In any case where AEs are unresolved at the time of study exit, this shall be documented on the eCRF.

The investigator is responsible for reporting AEs to Medtronic and their local IRB (per IRB reporting requirements) as outlined in Table 7 below, by completing the Adverse Event eCRF and/or Device Deficiency eCRF. For the purposes of this CIP, planned/elective procedures for pre-existing conditions are not considered or reported as AEs as long as the pre-existing condition is not aggravated or exacerbated after a study procedure. A list of AEs that may be associated with the device and/or the interventional procedure is provided in Section 10.1.

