4.3.1 Ancillary Endpoints

The following ancillary endpoints to be evaluated in this study are as follows:

1. Functional Patency Rate Through 12 months: *Defined as freedom from access abandonment from the time of first two-needle cannulation.*
2. Physiological Maturation Rate at 3, 6, and 12 months: *Defined as the percentage of access sites with access vessel minimum blood flow rate $\geq 500\text{mL/min}$ and minimum diameter $\geq 5\text{mm}$ as measured by duplex ultrasound.*
3. Functional Cannulation Success Through 12 months: *Defined as the time to achieve successful use of the endovascular AVF, with two-needle access and at least two hours of dialysis through the access, for more than two-thirds of the dialysis sessions over a continuous 28-day period after access creation.*
4. Days of Central Venous Catheter (CVC) Exposure through 12 months
5. Subject Satisfaction using the Vascular Access Questionnaire (VAQ) at 6 months
6. Nurse-Cannulator Satisfaction at 3, 6, and 12 months
Subjective and objective parameters will be assessed including fistula characteristics, cannulator training, skills and experience cannulating this type of fistula.

5. Investigation Plan

This study is a prospective, non-randomized, multi-center, single-arm, observational, post-market surveillance (PS) study of the Ellipsys Vascular Access System. The study will be conducted by newly trained providers in subjects on hemodialysis and medically indicated for creation of an upper limb anastomosis. Subjects will be followed for 12 months (+2 month window) following the AVF creation procedure.

6. Determination of Sample Size

The sample size is not driven by a statistical hypothesis. To ensure that a minimum of 100 subjects will be evaluable at the 12-month follow-up visit, a minimum of 134 subjects will be enrolled in the study. This sample size estimate allows for a 25% drop-out rate ($100/.75 = 134$ subjects) which may result due to a higher than normal attrition rate seen in this study population due to the natural history of the disease state. Newly trained users from up to 14 sites in the United States will participate in the study. Each study site will enroll no more than 20% of the total enrollment (134 subjects), with a maximum of 27 subjects.

7. Statistical Methods

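### SAP 7.8.3 counts anyone who starts an interval as observed to its end, so crude cumulative and after-3-months AE percentages are too low for subjects lost alive, by an amount that depends on when and why they leave

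*SAP*

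**What the plan says.** SAP 7.8.3 (Secondary Objective #4, overall patient safety) reports AEs as counts and crude percentages: "AEs will be summarized as the number of events as well as the number and percentage of subjects" with each type of event. The summaries are given cumulatively and for three periods: the first 7 days, "Post-operative: 8 days to 3 months after the AVF creation procedure", and "Follow-up: more than 3 months after the AVF creation procedure". The last period has no stated end.

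The denominator rule opens with "For the four different study intervals", which counts the cumulative summary as one of the four. It then says that "subjects are included in the denominator of percentage calculations if their follow-up has extended at least to the beginning of that study time interval".

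Observation stops at exit. Protocol 11.5 states: "Reporting of AEs and DDs shall end once the subject exits the study".

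The only attrition figure is in SAP Section 6: "This sample size estimate allows for a 25% drop-out rate". It is put down to the natural history of the disease. No timing and no split between deaths and other exits is given.

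Elsewhere the SAP does allow for unequal follow-up. SAP 7.8.2 uses Kaplan-Meier for study-related SAEs, with a cumulative-incidence sensitivity analysis. SAP 7.7.4 gives secondary procedures per person-years.

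**The concern.** A subject who exits alive on day 95 stays in the denominator of the after-3-months column for its whole length of about nine months, although only a few days of it were observed. A subject who leaves in week 2 stays in the cumulative denominator. Events after exit cannot enter the numerator, so the percentage can only fall.

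Device and procedure failures add to this. They belong to the Safety population (SAP 7.1.3), but Protocol Section 9 describes 12-month follow-up for subjects with a successful creation, and Protocol Table 2 marks no subject-visit form for the failures. They may bring little observed time to the cumulative denominator.

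Long-term safety is part of the primary objective. All-cause SAEs, non-serious related AEs, cannulation-related AEs and stenosis AEs are summarised as adverse events only in these tables, with no exposure-based or censoring-adjusted measure beside them.

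**Working it through.** **The plan's own figure.** 100/0.75 = 133.3, rounded up to 134, and 134 x 0.75 = 100.5. The enrolment target reproduces. The documents state no AE percentage or bias to reproduce.

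**Inputs from the documents.** 25% drop-out by 12 months (SAP Section 6); intervals of days 0-7, day 8 to 3 months, and after 3 months (SAP 7.8.3), taken here as days 0-7, 8-90 and 90-360; cumulative as days 0-360.

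**Assumptions, not in the documents.** Exit timing, share of deaths, AE risk and hazard shape. Each is varied below. Loss is taken as non-informative.

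**Formula.** Let G(t) be the probability of still being followed at day t and f(t) the density of the first event. For an interval from a to b, the expected crude proportion is the integral of f(t)G(t)/G(a) from a to b. The comparator is the risk under full follow-up, 1 - exp(-H), where H is the total hazard over the interval.

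**Rare events, even exits.** Here G(t) = 1 - 0.25t/360, and the ratio of crude to true is the mean of G over the interval divided by G(a).
- Cumulative: (1 + 0.75)/2 = 0.875, a shortfall of 12.5%.
- After 3 months: G(90) = 0.9375 and G(360) = 0.75, so 0.84375/0.9375 = 0.90, a shortfall of 10%.
- Day 8 to 3 months: G(8) = 0.9944, so 0.9660/0.9944 = 0.971, a shortfall of 2.9%.

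**Relative shortfall for non-fatal exits, constant hazard, true risks from 1% to 50%:**

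| Exit timing | Cumulative | After 3 months | Day 8 to 3 months | Days 0-7 |
|---|---|---|---|---|
| Even (uniform or exponential) | 11-13% | 9-10% | 2.5-3.2% | 0.2-0.3% |
| All in last 3 months | 2-3% | 3-4% | 0% | 0% |
| All in first 3 months | 21-22% | 0% | 10-12% | 1% |

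**Absolute size, even exits.** A true cumulative risk of 10% is reported as 8.7-8.8%, and a true 30% as 26.3-26.5%. After 3 months, 10% is reported as 9.0% and 30% as 27.2%.

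**Part of the drop-out is death.** With exponential exits, the total exit hazard is L = -ln(0.75)/360 per day. With AE hazard h, death share s and interval length T, the cumulative incidence is h/(h + sL) x (1 - exp(-(h + sL)T)). The crude proportion is the same expression with s = 1. Shortfall for true risks of 1% and 30%:

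| Deaths among exits | Cumulative | After 3 months |
|---|---|---|
| 0% | 13.1%, 12.4% | 10.0%, 9.5% |
| 25% | 9.9%, 9.4% | 7.6%, 7.2% |
| 50% | 6.7%, 6.3% | 5.1%, 4.8% |
| 75% | 3.4%, 3.2% | 2.6%, 2.4% |
| 100% | 0% | 0% |

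**Early-clustered AEs.** With 50%, 70% or 90% of the AE hazard in the first 30 days and even non-fatal exits, the cumulative shortfall falls to about 6-7.5%, 4-5% or 2%.

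**The case against.** The strongest reply is that many of the exits may be deaths. Protocol 3.1 says that one fifth of hemodialysis patients die each year, and the SAP ties attrition to the disease itself. A subject who has died belongs in the denominator of a cumulative incidence. If 20 of the 25 points were deaths, the rare-event arithmetic compares 0.875 with 1 - 0.20/2 = 0.90, a shortfall of about 3%. The one-year life-expectancy criterion may lower the death share, but no figure is given. This stands: it limits the size but does not remove the bias for subjects lost alive.

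Three further points also stand.
- Protocol Table 6 attributes AEs within 30 days to the index procedure by default, so procedure-related rows are less affected. That does not carry over to cannulation AEs, which need a mature fistula.
- A fatal AE is itself an SAE (Protocol Table 5), so in the all-SAE row a subject who dies normally counts as an event.
- The bias is modest beside sampling error: at 12/134 the Wilson 95% half-width is about 4.9 points, against a bias of about 1.2.

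A reader might infer more than the documents support.
- That late AE frequencies will be 10-12% too low. That is one scenario, and the plan gives neither exit timing nor death share.
- That the primary SAE endpoint is biased in the same way. It is not: SAP 7.8.2 censors, and adds subcomponents by device, study procedure and secondary procedure.
- That the crude tables will visibly contradict the Kaplan-Meier estimate. No row in 7.8.3 is clearly the same quantity as study-related SAEs, so a difference would not by itself show bias.
- That the pre-market comparison is undermined. It covers only the peri- and post-operative intervals.

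**Conclusion.** The point holds as a matter of direction and of missing analysis. Followed as written, the rule understates cumulative and after-3-months AE risk whenever subjects are lost alive, and the cumulative risk also where failures contribute little observed time.

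The size is conditional. Up to about 11-13% (cumulative) and 9-10% (after 3 months), relative, requires 25% drop-out, evenly spread non-fatal exits, constant hazard and true risks of up to 50%. It is about 5-7% if half the exits are deaths, near zero if all are, and about 0-22% across the exit timings tried. The effect on the pre-market comparison is about 3% or less with even exits; the post-operative part would reach 10-12% only if every exit fell in the first three months.

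No primary endpoint or formal test is affected. It is still worth correcting, because these tables carry most of the late AE information and the SAP already handles unequal follow-up elsewhere.

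**What to change.** Keep the crude counts and percentages, and add to SAP 7.8.3:

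- For the summary event-type rows (not every system organ class or event row) in the cumulative and after-3-months columns: events per 100 person-years of observed follow-up within the interval. This also deals with failures who have little exposure, and with completers whose 12-month visit falls anywhere up to day 420 (Protocol Table 3).
- For the main cumulative rows: a 12-month cumulative incidence with loss to follow-up censored and death as a competing event. The code in SAP 7.8.2 can be reused; there it serves as a sensitivity analysis, with any death as the competing event.
- In the all-SAE row, count a death that is the outcome of an SAE as an event, not as a competing event.
- If a cumulative incidence is also given for the after-3-months column, start it from a 3-month landmark among subjects still followed then.

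The cost is a little extra programming, mostly from dates already collected, and slightly less favourable rates.

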7.8.4 Ancillary Objective #4

Days of Central Venous Catheter Exposure Through 12-months

Analysis Dataset:

Safety Analysis Set per section **Error! Reference source not found..**

Analysis Method:

CVC use and exposure during the study will be summarized descriptively for subjects in the Safety population. The summary will include the number and percentage of subjects with CVC use during the study, broken down as:

- CVC present at study procedure
- CVC placed prior to AVF maturation
- Additional CVC placed during the study

The overall CVC exposure in days will be summarized descriptively.

Endpoint Definition:

Days of CVC exposure through 12 months.

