### Analysis Methods:

CVC use and exposure during the study will be summarized descriptively for subjects in the Safety population. The summary will include the number and percentage of subjects with CVC use during the study, broken down as:

- CVC present at study procedure

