***Medtronic Business Restricted***

## 13.5 Sample Size Determination

The sample size is not driven by a statistical hypothesis. To ensure that a minimum of 100 subjects will be evaluable at the 12-month follow-up visit, a minimum of 134 subjects will be enrolled in the study. This sample size estimate allows for a 25% drop-out rate ( $100/.75 = 134$  subjects) which may result due to a higher than normal attrition rate seen in this study population due to the natural history of the disease state. Newly trained users from up to 14 domestic centers will participate in the study. Each study site will enroll no more than 20% of the total enrollment (134 subjects), with a maximum of 27 subjects.

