7.2 General Methodology

For continuous variables, the number of observations, mean, standard deviation (SD), median, minimum, and maximum will be calculated, unless otherwise stated. For categorical variables, frequencies and percentages will be calculated. Exact binomial confidence limits will be calculated based on Wilson-score methods.

Survival analysis will also be performed for time-to-event endpoints using the Kaplan-Meier method. In cases where adjustment for competing risks is necessary, cumulative incidence curves will also be provided.

To assess the continued safety of the AVF creation procedure post-market, a subset of study endpoints will be descriptively compared to the pre-market study (DEN170004) results where possible. Comparisons will be performed using the Safety population for each study.

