7.7.4 Secondary Objective #3

Rate of Secondary Procedures

Analysis Dataset:

Treated Analysis Set per section **Error! Reference source not found..**

Analysis Method:

Secondary procedure rate will be summarized cumulatively through 12 months as the number of procedures per person-years as well as the number and percentage of subjects having one or more procedures in the Treated population. This summary will be presented overall and by type of procedure (surgical or percutaneous). Additionally, the number of secondary procedures will be summarized categorically as the number and percentage of subjects with 0, 1, 2, 3, or 4 or more procedures.

Summaries specific to PTA/balloon maturation interventions will be provided. These summaries will be based on secondary procedures that include a PTA/balloon maturation intervention, whether performed alone or in combination with other interventions. The summaries will be presented for interventions performed post-AVF creation through 12 months. The summaries will include the number of PTA interventions performed, whether the PTA was performed in combination with other interventions, the rate of intervention in person-years, the location and average balloon size. Similar summaries will be provided for stent, embolization, and valvulotomy interventions, presented cumulatively through 12 months.

This endpoint will also be summarized by type of procedure (e.g. banding, balloon maturation, transposition/elevation/ superficialization, etc.), indication (due to stenosis, due to AE, etc.), procedure success and association with any AEs.

Endpoint Definition:

Secondary procedures are surgical or percutaneous interventions designed to mature or maintain the AVF or re-establish flow. Secondary procedures are procedures subsequent to completion of the AVF creation procedure.

Additional Analysis:

- The association between the occurrence of acute anastomotic disruption or pseudoaneurysm and the secondary procedure rate for the Treated population. The mean number of secondary procedures will be summarized cumulatively and stratified by subjects who experienced anastomotic disruption or pseudoaneurysm and those who did not.
- The association between the occurrence of early occlusions and the secondary procedure rate for the Treated population. The mean number of secondary procedures will be summarized for subjects who experienced an early occlusion and those who did not.

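### Catheter exposure is summarised as raw days with no account of follow-up length, so subjects who leave early with a catheter in place pull the 12-month figure down

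*SAP*

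**What the plan says.** SAP 7.8.4 defines the endpoint as "Days of CVC exposure through 12 months", and Protocol 13.4.4 matches it. On method, both documents say that "CVC use and exposure during the study will be summarized descriptively for subjects in the Safety population". They break down the number of subjects with a catheter by when it was present or placed, and then add for the day count: "The overall CVC exposure in days will be summarized descriptively".

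SAP 7.2 sets the default for such a variable: "For continuous variables, the number of observations, mean, standard deviation (SD), median, minimum, and maximum will be calculated, unless otherwise stated". Section 7.8.4 states nothing different, so the natural reading is one day count per subject, averaged.

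The section gives no follow-up denominator, no exact cut-off day, and no rule for death, withdrawal or loss. The rule on death and loss in SAP 7.3 applies to endpoints analysed as time to event, which this one is not. Its missing-data rule excludes missing values but does not address a count that was cut short.

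Incomplete follow-up is expected. Protocol 13.5 says "This sample size estimate allows for a 25% drop-out rate", and attributes the attrition to the course of the disease. Elsewhere the SAP does account for follow-up: secondary procedures are given as "the number of procedures per person-years" (SAP 7.7.4), and the adverse-event intervals in SAP 7.8.3 count only subjects whose follow-up reached the interval.

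**The concern.** A count of days through 12 months is complete only for a subject observed for 12 months. For anyone who leaves with a catheter still in, the recorded count is only a lower bound. Take a subject who withdraws on Day 60 with a catheter in place and a completer whose catheter came out on Day 120. They contribute 60 and 120 days, so the first looks better although that subject's catheter use had not ended.

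Averaged over the study, the summary falls as attrition rises, whatever the fistula achieves. A reader would take the figure as the catheter time that subjects still face in the year after creation. It would understate that time, in the device's favour.

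**Working it through.** **The plan's own figure.** SAP section 6 aims "To ensure that a minimum of 100 subjects will be evaluable at the 12-month follow-up visit" and concludes that "a minimum of 134 subjects will be enrolled in the study". 100 / 0.75 = 133.3, rounded up to 134. This reproduces, so 25% is the planned attrition.

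**Inputs.**
- From the documents: 25% exit; 12-month target at Day 360 (Protocol Table 3).
- Assumed: every subject has a CVC at entry; removal times are exponential with median 90, 120 or 180 days; exit has a constant hazard and is unrelated to catheter status. If only a fraction had a catheter at entry and the rest never did, both means would scale by that fraction and the percentages would not change.

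**Formulas.** Removal hazard λ = ln 2 / median. Exit hazard μ = −ln(0.75) / 360 = 0.000799 per day. Mean days accumulated to Day 360 when the catheter time ends at total hazard h:

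M(h) = (1 − e^(−360h)) / h

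- Full 12-month mean, all exits treated as censoring: M(λ)
- Mean of raw recorded days: M(λ + μ)
- Mean counted to death, half of exits being deaths: M(λ + μ/2)

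At a 120-day median, λ = 0.005776:
- M(λ) = 0.875 / 0.005776 = 151.5
- M(λ + μ) = (1 − 0.125 × 0.75) / 0.006575 = 137.8
- M(λ + μ/2) = (1 − 0.125 × √0.75) / 0.006176 = 144.4

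| Median removal | Raw mean | Full 12-month mean | Shortfall | Mean to death (half of exits) | Shortfall |
|---|---|---|---|---|---|
| 90 days | 112.1 | 121.7 | 7.9% | 116.8 | 4.0% |
| 120 days | 137.8 | 151.5 | 9.0% | 144.4 | 4.5% |
| 180 days | 174.7 | 194.8 | 10.3% | 184.3 | 5.2% |

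**Other exit patterns.**
- If every subject has the same catheter duration c and the 25% leave uniformly over 360 days, the raw mean is 0.75c + 0.25(c − c²/720). For c = 120 this is 115.0, a shortfall of 4.2%. For c from 60 to 360 the shortfall runs from 2.1% to 12.5%.
- If the exit hazard is doubled while a catheter is in (simulation, 120-day median), the raw mean is 132.8 against 151.6, a shortfall of 12.4%.

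The direction is the same throughout. The size depends on the model.

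**Does the replacement work?** Sum, over the 360 days, the proportion with a CVC among subjects under observation that day. In simulation at the 120-day median this returns about 151 days when exit is unrelated to the catheter, and 147.7 against 151.6 under the doubled hazard. It removes all of the shortfall in the first case and most of it in the second.

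**Would a crude rate do?** Mean follow-up is M(μ) = 0.25 / 0.000799 = 312.8 days. Then 137.8 / 312.8 × 360 = 158.6 days, against 151.5. The crude rate over-corrects, because catheter use is early and the follow-up lost is late.

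**The case against.** **Death is not simply missing data.** Days lived with a catheter before death are a legitimate descriptive quantity, and crediting dead subjects with catheter time to Day 360 overstates the shortfall. This stands, and it is why two ranges are given. If 80% of exits were deaths, the target at a 120-day median would be 140.4 and the shortfall 1.8%. The share of deaths is an assumption in either case.

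**Failed creations.** A reader might infer that device and procedure failures, which the Safety population may include, enter as zero catheter days and make the shortfall far larger. With an assumed 5% of failures on a catheter all year, successes averaging 120 days and no other drop-out, the mean would be 114 against 132, or 13.6% low. The documents do not support this. No section scores failures as zero, and SAP 7.3 points to excluding missing values. Nor do they settle that such data are absent. In Protocol Table 2 the Safety Population row requires the Dialysis Catheter Use form, while the Device Failure and Procedure Failure rows leave it blank. That is an inconsistency to reconcile. If failures are excluded as missing, the same example gives 120 against 132, 9.1% low, but the failure rate is still assumed. Neither figure is part of the conclusion.

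**The visit window.** One might also infer that counting runs to Day 420, the end of the last window. The endpoint itself says through 12 months; only the exact cut-off day is missing.

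**Importance.** This is one of six ancillary descriptive endpoints. It has no formal test and is not among the planned comparisons with the pre-market study. Deaths, early terminations and visit compliance will be reported separately. All this limits the consequence but does not make the mean estimate what its title says.

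**Conclusion.** The concern holds. As written, the summary averages truncated counts under a 12-month label, and the result is biased low. Under the stated assumptions the shortfall is about 8-10% when all exits are treated as censoring, and about 4-5% when half are deaths and days are counted only to death. These sizes are illustrative: the documents give no catheter figures, and 25% is a planning allowance, not an observed rate. A better estimate is available at little cost, so the change is worth making. No primary result, safety conclusion or sample size depends on it.

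**What to change.** Amend SAP 7.8.4 and Protocol 13.4.4 as follows.

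1. Count CVC days from Day 0 to Day 360 only.
2. Keep the raw summary, and show follow-up time and the number with complete follow-up beside it. Add mean CVC days through 12 months, computed as the sum over Days 0-360 of subjects with a CVC that day divided by subjects under observation that day. Treat loss and withdrawal as censoring.
3. State how death is handled. One option is a main estimate with days counted to death, which multiplies each day's proportion by the Kaplan-Meier probability of being alive on that day, and a sensitivity estimate with death censored.
4. Do not rely on crude CVC days per follow-up day.
5. Keep the Safety population. Moving to the Treated population would drop the subjects left without a study fistula. Reconcile Protocol Table 2, and report the number of device and procedure failures and their CVC status at exit separately, not as zero days.

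The cost is wording in two documents and a short program. It needs catheter start and stop dates; the documents name the Dialysis Catheter Use form but do not show its fields, so this should be confirmed. Reconciling Table 2 may add a form for failed creations. The reported exposure will look somewhat higher than under the present wording.
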